9. RISK ANALYSIS

The decision to repair an aortic aneurysm is generally based on the risk of rupture, the risk of complications of surgery, and patient preference. There are currently two methods used to repair aortic aneurysms. The most common and conventional method is an open surgical repair, with the implantation of a synthetic graft to replace the diseased aneurysmal vessel through a large abdominal incision. Recent technological developments have resulted in an alternative, minimally invasive, endovascular aneurysm repair, in which a stent graft is placed within the aorta through a small incision in the groin. Blood can then flow through the stent graft and is excluded from the aneurysmal portion of the aorta.

The disadvantages of open surgical repair are: general anesthesia is required, it is a major abdominal surgery (large incision), has a significant surgical complication rate, and typically requires a long hospital stay and recovery. EVAR enables local or regional anesthesia to be used, uses a minimally invasive groin incision for catheter-based access, and has been reported in US clinical studies to offer a lower operative complication rate, reduced blood loss and procedure times, and shorter hospital stay. In contrast to open repair, EVAR is a relatively new treatment, long term results have not been fully established, and life-long surveillance is recommended to verify stent graft integrity and patency and continued aneurysm exclusion. Currently, five device systems are FDA-approved and marketed in the US for endovascular infrarenal abdominal aortic aneurysm repair. All of these devices require the introduction of catheter-based treatment devices varying in outer diameter profile from 20Fr to 25Fr (ipsilateral). Standard vascular exposure is indicated for access. Prospective clinical study results support the safety and effectiveness of these stent grafts through early follow-up (to 30 days) and in late follow-up to one year and to up to five years. These and other devices are CE Marked and are available in other international regions. One custom device is available in Europe for JAA endovascular repair; however, no ‘off-the-shelf’ endovascular devices are currently commercially available. No device is currently approved in the US for the endovascular repair of juxtarenal or pararenal aortic aneurysm.

As with any procedure there are risks of serious complications, such as death. The inclusion and exclusion criteria for this population have been carefully established to limit the risk of mortality and morbidity in this population. The overall risk will be evaluated on an individual basis and discussed with each patient. All of the potential adverse events outlined previously could cause prolonged illness, permanent impairment of daily function or, in rare cases, death. Possible treatments could include, but are not limited to, emergency cardiac or vascular surgery.

Eligibility criteria that exclude patients who are at higher risk for experiencing an anticipated adverse event have been selected to reduce the potential risks to patients who participate in this study. In addition, the assessment of patient anatomy for enrollment by an experienced Core Laboratory is also intended to reduce the potential risks to patients who participate in this study.

Pre-procedural high resolution, contrast-enhanced CT scanning and intraprocedural arteriography will be used to identify and target the aortic anatomy to facilitate the proper introduction, delivery, and deployment of the endovascular repair devices. Physician experience, rigorous application of a common protocol, and careful performance of the procedure with close monitoring of the patient after the procedure will also help to minimize risks.

The alternative to endovascular repair of JAA/PAA is open surgical repair.

10. STATISTICAL PROCEDURES

10.1 ANALYSIS POPULATIONS

All primary analyses will be conducted on an intention to treat (ITT) basis with imputation for missing data as described in the Patient Accountability and Missing Data section below. Whereas ITT is a concept intended to be applied to randomized trials, its use in this analysis will imply that patients will be analyzed based on the attempt to implant trial devices during the procedure. Patients who complete the trial through 12 months will comprise the completed cases (CC) population. CC patients who do not have protocol violations that can affect outcome will comprise the per protocol (PP) population. Additional analyses will be conducted in the CC population.

10.2 PATIENT ACCOUNTABILITY AND MISSING DATA

The proportion of patients with documented follow-up at each interval will be presented descriptively. The number of diagnostic, laboratory, and clinical evaluations will be tabulated by follow-up interval. Also, a listing of patients who initially consent but do not undergo a procedure due to withdrawal of consent will be given. However, these patients will not be included in any analysis.

Information on missing or withdrawn patients will be tabulated presenting the number and proportion of patients eligible for and compliant with each follow-up examination. Patients who withdraw from the trial will be tabulated with the reasons for the withdrawal. Additional sensitivity analyses will be performed as described below.

The evaluation of patients with missing data presents a special concern in ITT analyses. All clinical studies analyze the results based on the completed cases (i.e., those who complete the trial). Because missing patients do not have final data, they present a problem for ITT analyses. The statistical community recommends that multiple sensitivity analyses be conducted to determine the robustness of the result in patients who complete the study.^{10,11,12,13} The intention of these analyses is to demonstrate that the results obtained from the evaluable patients are not biased.

As a result, sensitivity analyses using multiple imputations will be conducted to evaluate the robustness of the study result accounting for missing observations. The primary effectiveness endpoint analysis will be based on an unbiased imputation of the determination of success or failure. It is expected that the number of patients with missing effectiveness data at one year will be approximately 15 patients (i.e., 15%). The missing value for these patients will be assigned by a simple random sample from the patients with outcomes at one year. This system is denoted the “Hot

¹⁰Pocock S. (1983). *Clinical Trials (A Practical Approach)*. John Wiley and Sons, Chichester.

¹¹Friedman L, Furberg C, and DeMets D. *Fundamentals of Clinical Trials*. 1985: Mosby Year Book, St. Louis.

¹²Guidance for Industry: E9 Statistical Principles for Clinical Trials. U. S. Department of Health and Human Services, Food and Drug Administration, Center for Drug Evaluation and Research and Center for Biologics Evaluation and Research. International Committee on Harmonization, September 1998.

¹³Rubin D. *Multiple Imputation for Nonresponse in Surveys*. 1987: John Wiley and Sons, New York.

Deck by Simple Random Sampling with Replacement".¹⁴ The number of patients to impute is small and trying to provide a more sophisticated imputation method would require modeling missingness with only approximately 15 patients or less with missing data. Additional sensitivity analyses will be done by using other imputation methods. The first shall be the last observation carried forward (LOCF). Another sensitivity analysis will entail considering the subject lost to follow-up to have failed the endpoint. A third analysis will impute the missing result as having succeeded the endpoint. A final analysis will impute the missing value by a generating a random number and comparing it to the value of the performance goal for effectiveness.

A comparison of baseline characteristics of the patients with missing data and those without missing data will be done to determine if there is evidence that the data are not missing at random (it is not possible to determine that data are missing at random). If the missing at random assumption is clearly violated by these comparisons, it is usually possible to find a sub-group that are not missing at random who have to be imputed differently, such as assigning the worst score to patients in the sub-group. For example, the proportion of patients missing an outcome may be much greater at a given study site which may also have a higher rate of failure. Those patients from that site may be assigned a failure and the baseline comparisons of the remaining patients will be rechecked to see if the imbalances are resolved. If this resolves the missing at random difficulty, the sub groups will be given special scores and the remaining patients will be imputed as described above. The resolution of the imbalance will be retested by the same methods with the patients identified above removed.

The primary imputation will be done 10 times with 10 different seeds to initiate the random selection and the combined P-value for the 10 imputations will be obtained by a method described in Rubin (1987) and in the SAS manual for PROC MIANALYZE. The seeds to be used for the 10 imputations are selected from a pseudo-random number table in Steele and Torrie (1960) and are 70303, 18191, 62404, 26558, 92804, 15415, 02865, 52449, 78509, and 43896.¹⁵

With regard to imputation for the primary safety endpoint, that endpoint is obtained so close to the procedure that there will be very little missing data, if any. In the control group, no patients were censored without an MAE through 30 days. If any of the test patients are lost to follow-up prior to 30 days, that patient will be assigned an MAE for primary analysis purposes.

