10.7.2 Sample Size

The primary trial effectiveness variable is the Treatment Success rate at one year post-operatively. Treatment Success is a composite of clinically-relevant outcomes, including procedural technical success and absence of: aneurysm rupture, conversion to open repair, Type I endoleak after 30 days; Type III endoleak; clinically significant migration; aneurysm enlargement; or secondary intervention for resolution of endoleak, limb occlusion, migration, aneurysm sac expansion and/or a device defect.

The sample size is obtained by using the exact binomial distribution using PASS 2008. A sample size of 82 patients at one year in the test group will have 80.58% power against a null performance goal of 80% if the proportion of Treatment Success is 90% or higher for alpha = a one-sided 0.05. It is estimated that the rate of Treatment Success will be greater than 90%.

It is anticipated that the drop-out rate of the trial will be 15% or less. Because the larger of the two sample sizes after adjustment for loss to withdrawal is the one for effectiveness, $82/0.85 = 97$ patients will need to be recruited for this trial.

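### The primary hot deck ignores status already observed, and the plan does not say whether a component failure documented before loss stands

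*Combined protocol and SAP*

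**What the plan says.** Section 10.2 expects about 15 patients (15%) without effectiveness data at one year and describes the primary imputation as unbiased. The rule is: "The missing value for these patients will be assigned by a simple random sample from the patients with outcomes at one year". Sampling is with replacement, and "The primary imputation will be done 10 times with 10 different seeds to initiate the random selection", with the results combined by Rubin's method. The reason given for keeping it simple is that "trying to provide a more sophisticated imputation method would require modeling missingness with only approximately 15 patients or less with missing data".

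Earlier observations enter only through last observation carried forward, which is a sensitivity analysis. Missing-as-failure is also a sensitivity analysis: "Another sensitivity analysis will entail considering the subject lost to follow-up to have failed the endpoint". There is one exception inside the primary imputation. If comparing baseline characteristics suggests that data are not missing at random, the plan holds that "it is usually possible to find a sub-group that are not missing at random who have to be imputed differently", for example by scoring a site's missing patients as failures.

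Section 10.7.2 defines Treatment Success as a composite "including procedural technical success and absence of: aneurysm rupture, conversion to open repair", and of further endoleak, migration, enlargement and reintervention events. Section 8.7.7 places technical failure within 30 days of the procedure. Nothing in sections 6.2, 8.7.7, 10.2 or 10.7 says how to classify a patient who has a documented component failure and is then lost.

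**The concern.** The composite requires the absence of events, so one component event settles the outcome as failure. For technical failure, conversion or reintervention this can be known months before one year. The imputation rule does not use that information, either to fix a failure or to choose donors for a patient known to be failure-free so far.

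The protocol can produce such patients. Section 10.1 analyses patients by attempted implant, while section 8.6.9 lets a patient exit when the device is not implanted. Section 8.6.8 declares loss only after two consecutive missed visits, so a patient lost at one year may have a one-month CT on file. A converted patient may have no endograft left to image. At stake is the primary effectiveness test against 80%, which is narrow enough for one patient to decide it. How deaths are scored is a separate question and is not raised here.

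**Working it through.** **Plan's own figures.** Null 80%, alternative 90%, one-sided 0.05, 82 evaluable, 15% dropout (section 10.7.2). For n = 82 the smallest r with P(X ≥ r | 0.80) ≤ 0.05 is 72 (tail 0.0458). P(X ≥ 72 | 0.90) = 0.8057, against the stated 80.58%. 82/0.85 = 96.5, so 97. Both reproduce. For n = 97 the pass mark is 85 (tail 0.0346).

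**One patient at the margin.** Suppose 72 of 82 completers succeed (0.8780).
- All 15 missing drawn: 72 + 15 × 0.8780 = 85.17 on average, a pass (p = 0.035 at 85).
- One of the 15 is a documented failure and is kept: 72 + 14 × 0.8780 = 84.29, a fail (p = 0.062 at 84).

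**Literal reading.** Let p be true success, and let failures be missing with probability f and successes with probability s, where ps + (1 − p)f = 0.15. The documents give neither f nor s, so f is an assumption shown as a range. The expected estimate is close to the completers' success rate, p(1 − s)/0.85. At p = 0.80, with 200,000 simulated trials of 97 patients per row:

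| f | s | Completers' success rate | Passes, single draw, ≥85/97 | Passes, 10 draws, Rubin, z > 1.645 |
|---|---|---|---|---|
| 15% | 15% | 0.680/0.85 = 80.0% | about 6% | about 8% |
| 20% | 13.75% | 0.690/0.85 = 81.2% | about 9% | about 12% |
| 30% | 11.25% | 0.710/0.85 = 83.5% | about 21% | about 26% |
| 40% | 8.75% | 0.730/0.85 = 85.9% | about 40% | about 48% |

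In the first row there is no bias. The excess over 5% there comes from the draw and the normal approximation, not from this point.

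**Documented failures treated as known, event-free patients drawn from everyone with an outcome.** Take f = s = 15% and all failures before loss.
- p = 0.80: kept failures are 0.20 × 0.15 = 0.03 of patients, and event-free missing are 0.80 × 0.15 = 0.12. If the kept failures join the donors, the donor rate is 0.68/0.88 = 0.7727, and the estimate is 0.68 + 0.12 × 0.7727 = 77.3%. If donors are completers only, it is 0.68 + 0.12 × 0.80 = 77.6%.
- p = 0.90, kept failures among the donors: 0.765/0.865 = 0.8844, and 0.765 + 0.135 × 0.8844 = 88.4%.

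With 70% to 100% of failures before loss, the bias is 1 to 3 points downward. Simulated power at 90% (single draw, kept failures among the donors) is 66% to 71%, against about 80% for the literal draw.

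Failures that were never documented pull the other way. With f = 30%, 70% documented and completers as donors, the imputed share is 0.09 + 0.06 × 0.3 = 0.108. The estimate is 0.71 + 0.108 × 0.8353 = 80.0%: two opposite errors that happen to cancel.

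**Keep documented failures and match donors on visit status.** At p = 0.80, f = s = 15% and all failures before loss: donors are all successes, and 0.68 + 0.12 × 1 = 80.0%. With 70% before loss: the donor rate is 0.68/(0.68 + 0.17 × 0.3) = 0.930, and 0.68 + (0.12 + 0.009) × 0.930 = 80.0%. Simulated false-pass rate (single draw) is about 3.5% to 4%, with power of 82% to 83% at 90%. If failures are missing at 30% or 40% and only 70% precede loss, the false-pass rate is about 7.0% or 9.5%. That is much lower than under the literal rule, but not removed.

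**The case against.** The strongest reply is that a documented failure is not missing. The hot deck imputes a determination of success or failure, and a recorded conversion or reintervention already supplies one. Section 10.3 counts events up to day 365 whenever they occurred, and section 8.7.7 rests event analyses on committee categorization, so no one-year CT is needed. This is a sensible reading, and no sentence contradicts it. A reader might infer that the plan does redraw known failures. The documents do not support that: they leave the matter unstated. But the sensible reading is unwritten too, and adopting it without changing the donors produces the downward bias shown above.

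A reader might also infer, from last observation carried forward being only a sensitivity analysis, that the primary analysis discards known failures. That does not follow. Carrying forward would differ from the primary analysis even if known failures were kept, because it scores event-free dropouts as successes. Nor is every missing patient drawn this way, given the subgroup exception. That exception is triggered by baseline imbalance, however, and is not designed to detect a failure after the procedure.

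The missingness rates are assumptions, and the higher ones are severe. At f = 30% and 40%, 97 × 0.20 × f gives 5.8 and 7.8 failures among 97 × 0.15 = 14.6 missing patients. That stands.

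The plan's argument that 15 patients are too few to model is fair against a regression. It does not bear on keeping a known failure or on filtering donors by visit status. Drawing event-free patients from all donors can be called conservative, but it is still a bias and costs 9 to 14 points of power in the setting above. The sensitivity analyses would expose the problem but do not decide the primary result.

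**Conclusion.** The primary draw does not use observed status, and the plan does not settle whether a documented failure stands. When failures occur before loss, neither reading reliably gives the unbiased imputation that the plan describes. The literal reading favours the device if failures are missing more often. The known-failure reading pulls against the device through its donor pool. The exception is the literal reading with missingness unrelated to outcome, which is unbiased and only less efficient (about 80% power against 82% to 83%).

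The size cannot be fixed from the documents. A false-pass rate between about 6% and 40% (single draw), or 8% and 48% (Rubin combination with a normal z-test), rests on 15% overall missingness and failures missing at 15% to 40%. A reader might infer that the trial's result is biased toward the device. The documents support only that it could be, under one reading and one pattern of missingness.

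**What to change.** Replace the assignment sentence in section 10.2 with two rules:
- Any Treatment Success component failure documented before loss is a failure and is not imputed.
- A patient failure-free at the last completed visit (discharge, 1 month or 6 months) is imputed from patients with one-year outcomes who were failure-free at that same visit.

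Keep the ten imputations and the Rubin combination. Keep the other imputation methods as sensitivity analyses, since missing-as-failure still bounds the effect of undocumented failures, which this change cannot recover.

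The cost is two sentences of SAP text and slightly more programming. The visit and event data are already collected. The observed success rate may come out slightly lower.

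### Section 10.2 reads baseline differences as evidence against missing at random, then lets a subgroup found after the fact be scored (for example as failures) inside the primary effectiveness imputation

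*Combined protocol and SAP*

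**What the plan says.** Section 10.1 ties all primary analyses to the imputation in section 10.2. There the default for the effectiveness endpoint is a simple hot deck: "The missing value for these patients will be assigned by a simple random sample from the patients with outcomes at one year". It is run ten times with ten listed seeds and combined by Rubin's method. Four sensitivity analyses follow: last observation carried forward, all missing as failures, all missing as successes, and a random draw at the performance goal.

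The next paragraph is not one of those four. It compares the baseline characteristics of patients with and without missing data, looking for evidence that data are not missing at random. "If the missing at random assumption is clearly violated by these comparisons", a subgroup may be identified and imputed differently, the worst score being given as one possibility. The illustration is a site with far more missing outcomes, "which may also have a higher rate of failure", of which the plan says: "Those patients from that site may be assigned a failure and the baseline comparisons of the remaining patients will be rechecked to see" whether the imbalance is resolved. If it is, the subgroup keeps its special scores and only the remaining missing patients go to the hot deck.

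For this step section 10.2 states no covariate list, no test level, no definition of a clear violation, no timing and no blinding.

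**The concern.** There are two faults.

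**The inference does not follow.** Missing at random allows missingness to depend on observed baseline factors. A baseline difference between patients with and without an outcome therefore cannot show that missing at random fails. It can show that missingness is not completely random, and that is what an unconditional hot deck relies on when the factor also predicts success.

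**The remedy is discretionary and sits in the primary analysis.** Which patients enter the hot deck, and which receive a fixed score, is decided after looking at the data, with no stated criterion. In the plan's own example the site's failure rate is part of the reason for choosing it. Fixing ten random seeds in advance protects little if the set of patients to be imputed can change. In an open, single-arm trial with one primary effectiveness test, whether the trial passes could turn on that choice.

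**Working it through.** **1. The plan's own figure.** Inputs from section 10.7.2: goal 80%, alternative 90%, one-sided 0.05, 82 evaluable patients.
- P(X ≥ 72 | 82, 0.80) = 0.0458 and P(X ≥ 71 | 82, 0.80) = 0.0836, so the cut is 72.
- Power: P(X ≥ 72 | 82, 0.90) = 0.8057, against 80.58% stated.
- 82/0.85 = 96.47, rounded up to 97. So 97 − 82 = 15 are missing, which agrees with section 10.2.

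The design reproduces.

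**2. What the comparison can show.** Let R mark an observed outcome, Y the outcome and X the baseline factors.
- Missing completely at random: P(R | X, Y) = P(R).
- Missing at random: P(R | X, Y) = P(R | X).
- A baseline difference shows P(R | X) ≠ P(R). It contradicts the first line and is compatible with the second.
- Failure of the second line means dependence on the unseen Y given X, which no comparison of X can reveal.

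The plan's example fits this. A site with more missing outcomes and more failures is consistent with missing at random given site. Drawing donors within that site or site group would give its missing patients the site's own success rate. Scoring them all as failures gives them a success rate of zero.

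**3. Effect of reassignment.** Assumptions: 82 observed, 15 missing, m of the 15 set to failure, and the other 15 − m drawn at the observed rate in each of ten imputations. Estimates are combined by Rubin's rules and tested against 0.80 at one-sided 0.05. The plan does not say which within-imputation variance applies, so both are shown: null, 0.80 × 0.20/97; and observed, p(1 − p)/97.

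Chance of passing at true success of 90% (simulation):

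| m | null variance | observed variance |
|---|---|---|
| 0 | 81.3% | 86.8% |
| 1 | 74.1% | 81.0% |
| 2 | 65.6% | 73.4% |
| 3 | 55.5% | 65.3% |
| 5 | 33.0% | 42.8% |

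A single draw with an exact cut of 85/97 gives the same pattern: 79.9% (m = 0), 53.6% (m = 3), 31.3% (m = 5).

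**4. Direction.** At true success of 80%, the chance of a false pass falls from 5.1% (m = 0) to 1.0% (m = 3) and 0.2% (m = 5) with null variance. With one draw it falls from 5.8% to 1.1% and 0.2%.

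**5. At the boundary.** Suppose 72 of 82 succeed.
- No reassignment: expected total 72 + 15 × 72/82 = 85.2. At 85/97 the exact p is 0.035, a pass.
- Two set to failure: 72 + 13 × 72/82 = 83.4. At 83/97 the exact p is 0.104, a fail.

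**The case against.** - *The wording is hedged.* The plan speaks of evidence and a clear violation, concedes that missing at random cannot be established, and introduces the site by way of example with a permissive verb. This stands. Calling baseline differences proof would misstate the plan, and use of outcome data is shown only in the example. That outcomes would already be known is an inference from that example and from the lack of any blinding. By contrast, section 10.6.3 requires an independent statistician without outcome data for the safety propensity score.
- *Nothing observed changes.* Correct. Only patients without a one-year outcome could be rescored.
- *The other missing patients are not simply left with unsuitable donors.* They go to the hot deck only if balance is restored once the subgroup is removed. This also stands, although the plan is silent on what happens if balance is not restored.
- *The sensitivity analyses bracket the result.* They do, but they do not settle which result is primary. With 15 missing, the all-failure analysis cannot pass even if all 82 observed patients succeed: at 82/97 the exact p is 0.161.
- *About 15 missing patients cannot support a complex model.* Fair, and a reason to keep the primary method simple. It does not justify an open-ended search.

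**Conclusion.** The point holds as a fault in the stated rule and in its prespecification. The plan draws the wrong conclusion from baseline differences and allows a subgroup chosen after the fact to be rescored within the primary imputation. If three or five of 15 missing patients are set to failure at true success of 90%, the chance of passing drops by about 26 points (81.3 − 55.5) or 48 points (81.3 − 33.0) with null variance. With observed variance the drops are about 22 (86.8 − 65.3) and 44 (86.8 − 42.8). These figures assume 15 missing, a common success rate and failure as the assigned score.

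A reader might infer two stronger things that the documents do not support.
- *That the step favours the device.* Assigning failure lowers the false-pass rate. The plan's open wording on special scores does not limit them to failure, but it proposes no favourable score either.
- *That chance alone would trigger it in about half of trials.* Fifteen independent tests at 0.05 give at least one nominal difference with probability 1 − 0.95^15 = 53.7%. The level, the independence and the list of 15 (borrowed from section 10.6.3) are all assumptions. One nominal difference is also not the plan's clear violation, and reassignment further needs an identifiable subgroup and restored balance. The firing rate cannot be computed, so 53.7% must not be combined with the power losses.

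**What to change.** 1. Remove the search-and-reassign step from the primary effectiveness analysis. Keep it only as a labelled sensitivity analysis, beside the four already listed.
2. State one fixed primary imputation, with the ten seeds kept. If donors are to be matched, name one or two baseline factors chosen on clinical grounds and freeze them before one-year outcomes are released. The baseline comparison then becomes descriptive and has no power to change the primary method.
3. Replace not missing at random with not missing completely at random where the baseline comparison is described.
4. State which within-imputation variance the combined test uses, since the pass probabilities above depend on it.

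Cost: SAP wording and a small program change. The downside is smaller donor cells: with 82 observed patients, one two-level factor leaves about 82/2 = 41 donors per cell on average, and two such factors about 82/4 = 20.
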